Figure 3 describes the study flow. After potential subjects are identified based on inclusion and exclusion criteria, they will be asked to complete a number of questionnaires to obtain baseline information on PA, social participation and contextual environment. They will then be taught to wear a wrist-worn accelerometer for 7 days to monitor home activities. Subjects who successfully completed the baseline 7-day home monitoring will be randomized into 2 arms: intervention or wait- list control groups. The intervention group will receive the tailored PA report in a one-hour counseling session, followed by weekly phone calls for 4 weeks by the same occupational therapist. This will be followed by monthly phone calls by research assistants until the end of the study.

The wait-list control group will receive monthly phone calls to discuss about their health status but not PA-related issues. These monthly phone calls are necessary to maintain the subjects' interest in staying in the trial. The wait-list control will receive the tailored PA pattern report and the counseling intervention at the end of the study.

Both arms of the study will have post-intervention assessment at 5 weeks after randomization and final outcomes assessment 6 months after randomization. Each outcomes assessment involves surveys, physical function assessment, and a 7-day home monitoring period. After the 6-month assessment, we will interview participants who completed the intervention to assess their experience for the purpose of improving the intervention in the future.

Research Procedures

Baseline data collection: Aim 1

If potential participants meet the inclusion and exclusion criteria based on phone screening, then they will be invited for baseline evaluation. Baseline data collection will be completed in 4 steps from 3 sources: accelerometer-generated PA patterns, the ecological momentary assessment (EMA) of contextual environment, and survey data. We estimate the time to complete baseline assessment will be 1.5 - 2 hours.

1. After participants complete the screening and informed consent, a trained research assistant will assess their physical performance, which includes the Six-Minute Walk Test ⁶⁴ and Timed Up and Go Test ⁶⁵.

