5. After the face-to-face session, the same OT will make weekly phone calls to the participants for 4 weeks (See Appendix for a Flowchart of the Phone Call). The OT will already have been trained by [name] group to make these phone calls following the flowchart, demonstrated an understanding of the program, learned to address the various actions on the flowchart (i.e., how to probe for barriers, how to help with problem solving, etc.), and how to respond to participants' various questions. The OT will ask the participant questions based on their response to the PA worksheet as described above. Then, using the answers to the PA worksheet as a guide, the OT will review with participants the steps of the self-regulation, provide positive reinforcement, assess progress in achieving PA goals, problem solve barriers, and discuss changes in medications and health status. Each phone call will last approximately 30 minutes. This completes the intervention phase of the study.

Wait-list control group

This group will participate in all outcome assessments as the intervention group at baseline, post-intervention, and 3-months and final assessments. After the 6-month final assessment, these participants will receive their baseline activity summary reports and the counseling that the intervention group had received.

Post-intervention assessment

Post-intervention assessment will be done 5 weeks after randomization to assess if the intense intervention (counseling and weekly phone calls) had an immediate impact on the study participants. Potential participant drop outs are expected at the 6-month follow-up. Therefore, information obtained at the post-intervention assessment will be helpful in determining the impact of the intervention. All participants in the intervention group and wait-list control group will be assessed for all outcomes, including the 7-day home monitoring.

After the post-intervention assessment, a RA will contact all participants monthly until the 6-month final assessment to discuss changes in medications and health status. PA issues will not be discussed. The goals of these phone calls are to obtain updated health information and maintain the participants' interest in remaining in the trial.

Measures

Primary outcomes:

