1. The Six- Minute Walk Test⁶⁴ – A participant will be instructed to walk at his/her usual pace for six minutes and distance covered in feet is recorded.
2. Timed Up and Go Test⁶⁵ – A participant will be timed (in seconds) when get up from sitting in a chair, walk 3 meters, turn around, and walk back to sit down.
3. Comfortable gait speed in 10 meter walking.
4. Rosow, Breslau and Nagi activities⁸¹⁻⁸⁴ – Self-reported ability to run a mile, walk 1 or several blocks, sit for 2 hours, get up from a chair after sitting for a while, climb 1 or several flights of stairs, lift or carry over 10 lbs., stooping/crouching/kneeling, pick a dime up, reach or extend arms, and pulling/pushing large objects.

b) **Biomarkers:** A1c and body mass index will be assessed at baseline and at the final (or 6-month) follow-up. A1c measures average blood glucose level in the past 3 months. At the time when participants visit VA Ann Arbor for baseline and final assessment, they will be asked to go to the VA Ann Arbor's Ambulatory Care laboratory to have a random blood sample obtained by the staff to assess for A1c value. Standard scales used in Ambulatory care clinics will be used to measure the height and weight of each participant.

c) **Quality of life** will be assessed by VR-12, which is a well validated 12-item questionnaire that assesses both the physical and mental health quality of life of veterans.

d) **Participant retention** is the extent to which our program is able to retain the intended audience to complete the study.⁸⁶ Results from participation retention provide information on the acceptance of the intervention by the veterans. Retention can be calculated as [(participants completing post intervention assessment/participants enrolled) x 100].

e) **Intervention feedback** is an important goal for this pilot trial. It will inform the PI if certain part of the intervention should be revised, added, or removed to improve the intervention for future trials and for dissemination. The information will be obtained in two ways at the end of the study:

1. Participant satisfaction with the program, including participant perception of usefulness of proposed intervention, will be measured by a series of Likert scale satisfaction items adapted from the measures used by Schron et al.⁸⁷ (See Appendix).

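### The retention formula counts attendance at 5 weeks, although retention is defined as staying to the end of a 6-month study

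*Combined protocol and SAP*

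**What the plan says.** Measures, Secondary outcomes, item d describes participant retention as "the extent to which our program is able to retain the intended audience to complete the study". It gives the interpretation that "Results from participation retention provide information on the acceptance of the intervention by the veterans". One rule for computing it follows: "Retention can be calculated as [(participants completing post intervention assessment/participants enrolled) x 100".

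The timing of that assessment is fixed elsewhere. Participant Timeline gives both arms a "post-intervention assessment at 5 weeks after randomization and final outcomes assessment 6 months after randomization", so the two are separate visits. The section on the post-intervention assessment repeats the timing ("Post-intervention assessment will be done 5 weeks after randomization") and adds that "Potential participant drop outs are expected at the 6-month follow-up". In Table 3, as far as the extracted text can be trusted, retention carries a single mark under Post-intervention and none under 3 and 6 months.

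The denominator is not defined. Participant Timeline says "Subjects who successfully completed the baseline 7-day home monitoring will be randomized into 2 arms". The Randomization section says that randomization took place at enrolment, but also that assignment follows successful baseline data collection. The Aim 2 analysis paragraph speaks of everyone initially enrolled as having a randomized group.

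The Missing Data section will record reasons for loss and compare loss rates between arms with a chi-square test. It names no time point and does not mention the retention outcome.

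**The concern.** The description and the rule in the same item measure different things. A participant who attends at week 5 and leaves in month 3 has not completed the study, yet the formula counts that person as retained. The plan expects drop-out at 6 months, and this is the part of attrition that the formula cannot see.

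Retention is a named secondary outcome of a pilot that is meant to prepare a larger trial. Hypotheses 2a and 2b are both tested at 6 months, so 6-month attrition is what a successor with the same endpoint would need to allow for. A 5-week percentage labelled simply as retention could be taken for that number.

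The item also treats retention as evidence that veterans accept the intervention, but the formula pools the arms. The wait-list group receives the report and counseling only after the 6-month assessment, so its attendance at week 5 says nothing about accepting them.

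**Working it through.** **1. Is there a plan figure to reproduce?** No. The documents give no retention target and no drop-out rate. The nearest numbers are a total of 70 (Study Design) and a sample of 28 to 35 per treatment group (Hypothesis 2a). These fit together: 70/2 = 35 and 28/35 = 80%. The plan does not say that 28 is the number completing 6 months; that is an assumption made here for scale.

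**2. The two quantities.** Let N be the number randomized, E the number enrolled, C5 the number completing the 5-week assessment and C6 the number completing the 6-month assessment.

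- Formula in the plan: 100 × C5/E
- Retention to study completion: 100 × C6/N

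If E = N, the difference is 100 × (C5 − C6)/N. If everyone in C6 is also in C5, this is never negative, and it is positive as soon as one person leaves between the two visits. Someone who missed week 5 but returned at month 6 would break that condition.

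**3. Numerator effect.** Take E = N = 70 and assume C6 = 56 (28 per group). The C5 values are illustrative.

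| C5 | Plan's formula, C5/70 | 6-month retention, 56/70 | Difference (points) |
|---|---|---|---|
| 70 | 100.0% | 80.0% | 20.0 |
| 67 | 95.7% | 80.0% | 15.7 |
| 63 | 90.0% | 80.0% | 10.0 |
| 60 | 85.7% | 80.0% | 5.7 |
| 56 | 80.0% | 80.0% | 0.0 |

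The range is 0 to 20 points. The upper end needs every loss to fall after week 5.

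**4. Denominator effect.** Suppose instead that enrolled includes people lost before randomization. Keep N = 70, C6 = 56 and C5 = 67, with illustrative values of E.

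| E | Plan's formula, 67/E | Minus 80.0% (points) |
|---|---|---|
| 75 | 89.3% | +9.3 |
| 80 | 83.8% | +3.8 |
| 85 | 78.8% | −1.2 |
| 90 | 74.4% | −5.6 |

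The sign changes at E = 67/0.80 = 83.75. With C5 = 63 it changes at 63/0.80 = 78.75. A wider denominator therefore lowers the figure and can cancel or reverse the numerator effect.

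**5. Pooling effect.** If 28 of 35 in the intervention arm and 35 of 35 in the wait-list arm attend, the pooled figure is 63/70 = 90%, against 80% in the only arm that received the intervention. These counts are illustrative too.

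**6. Precision of the 6-month figure.** Under the same assumption, 56/70 = 80.0% has a Wilson 95% interval of 69.2% to 87.7%. Within one arm, 28/35 = 80.0% has an interval of 64.1% to 90.0%. The figure is imprecise enough to need its interval beside it.

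**The case against.** The strongest defence is that week 5 is the right time to judge acceptance. The section describing the intervention says that the four weekly therapist calls complete the intervention phase, and the later monthly calls avoid physical activity. Attendance at month 6 therefore partly reflects the burden of follow-up. The plan also explains why it has a 5-week assessment: later drop-out is expected, and these data will help to judge the intervention's impact. This supports keeping a 5-week figure, specifically in the intervention arm. It does not make that figure a measure of study completion, which is how item d describes retention, and it does not justify pooling the arms.

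Second, later losses are not ignored. The Missing Data section compares losses by arm, and the 6-month analyses will yield completion counts. A reader might infer that the larger trial will be planned with too little allowance for attrition. The documents do not support that, because the information would be available and no progression rule depends on retention. The defect lies in the named outcome.

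Third, a reader might infer that the enrolled denominator inflates the figure. It does not. If enrolled means randomized, as parts of the Randomization section and the Aim 2 paragraph suggest, it is neutral. If it includes people lost before randomization, it lowers the figure. What stands is ambiguity.

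Finally, the formula is worded permissively, as one way in which retention can be calculated. That is true, but no other way is given.

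**Conclusion.** The point holds: the only stated formula for retention does not measure retention as the plan describes it. On a common denominator, with 6-month completers also present at week 5, the formula gives a figure at or above 6-month retention, and above it if anyone leaves after week 5.

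The size is unknown. The range of 0 to 20 percentage points rests on reading 28 of 35 per group as 6-month completion, which the plan does not say. The upper end also assumes that all losses come late, so 20 points is not an expected error. A reader might go further and say that the published figure will overstate retention. The documents do not establish this, since they give no attrition rates and an enrolled total larger than the number randomized could reverse the sign.

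Two smaller points stand beside it: enrolled needs a definition, and the figure needs to be split by arm. No primary analysis is affected. The change should still be made, because a named outcome of a pilot should measure what it is said to measure.

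**What to change.** - In Secondary outcomes, item d, define retention as (randomized participants completing the 6-month assessment / participants randomized) × 100, reported by arm and overall with 95% confidence intervals.
- Keep the 5-week percentage as a separate, labelled number on the same denominator. Its intervention-arm value is the one that informs acceptance of the active phase.
- Define enrolled, and report people lost between consent and randomization (failed learning module, incomplete baseline monitoring) as a separate count.
- Add a 6-month mark for retention in Table 3.

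The cost is about one sentence and one table cell. The assessments needed are already planned, so there is no extra burden on participants. The downside is that the reported retention may be less favourable.

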Diverse event rates: Participants can report an AE event by phone or email or at the monthly follow-up phone calls. The AEs will be tracked electronically in a participant management system. Study-related AEs will be classified as serious if they require hospitalization or result in significant disability. All other study-related AEs will be classified as minor, resulting in minimal or no disability and not requiring hospitalization. If a participant experiences a severe symptomatic hypoglycemia, that participant will be temporarily suspended and will need to obtain medical clearance from his or her medical provider before resuming the intervention. The intervention clock will continue to run during the suspension and end of study will not be delayed.

g) **Medication changes:** The intervention may lead to increase physical activities, which may lead to lower blood glucose, lower blood pressure, lower cholesterol, all possible outcomes associated with regular physical activities. The subjects' health care providers are likely to make medication changes when glucose, blood pressure, and / or cholesterol levels are lowered with the progression of the study. Therefore, medications associated with lowering glucose, blood pressure, and cholesterol, will be assessed for changes by reviewing the subject's VA electronic medical record (CPRS).

Co-variates, predictors and confounders:

1. **Environment:** Contextual environment may be barriers or facilitators for PA and social participation, and will be assessed *at baseline* using a survey, momentary assessment using the Actiwatch, and data from logbook.

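### Early minor adverse events are open to ascertainment bias: in weeks 0-5 only the intervention arm has weekly staff contact about health, and no matching inquiry is set for the wait-list arm

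*Combined protocol and SAP*

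**What the plan says.** Under Measures, Secondary outcomes, the adverse event item gives the reporting routes without distinguishing the arms: "Participants can report an AE event by phone or email or at the monthly follow-up phone calls". It grades only study-related events, as serious or minor.

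Contact differs by arm early on. Participant Timeline gives the intervention arm a one-hour session, "followed by weekly phone calls for 4 weeks by the same occupational therapist". Item 5 of the intervention section sets each call at about 30 minutes and includes among its tasks to "problem solve barriers, and discuss changes in medications and health status".

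For the other arm, Participant Timeline says "The wait-list control group will receive monthly phone calls to discuss about their health status but not PA-related issues", with no start date. The Post-intervention assessment section dates the research assistant's calls: "After the post-intervention assessment, a RA will contact all participants monthly until the 6-month final assessment". These later calls are the same in both arms.

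The assessments are shared. Participant Timeline states "Both arms of the study will have post-intervention assessment at 5 weeks after randomization and final outcomes assessment 6 months after randomization", and the Wait-list control group section says "This group will participate in all outcome assessments as the intervention group", adding a 3-month visit. Table 3 marks adverse events at post-intervention, during the intervention, and at 3 and 6 months. They are the only row marked in the during-intervention column.

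The Secondary analyses section covers functional status, biomarkers and quality of life. It does not mention adverse events.

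**The concern.** When reporting is passive, the number of events recorded depends on how often a participant talks to staff about health. Strains, minor falls and mild low-glucose symptoms may well be mentioned within a week and forgotten by week 5. If only one arm has weekly conversations, it can show more minor events with no difference in true risk.

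The imbalance falls in the counselling phase, when activity is meant to change most. An artefactual excess could be read as harm. A real excess could be dismissed as the result of closer contact. The pilot is meant to prepare a larger trial, so its early safety description should not be ambiguous in this way. The protocol itself notes in its background that more intense activity may raise injury risk in older adults, and it makes provision for severe symptomatic hypoglycemia.

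**Working it through.** The documents give no adverse event rate or capture probability, so there is no stated figure to reproduce. The check has two parts.

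**1. Scheduled contacts** (Participant Timeline; intervention section, item 5; Wait-list control group; Post-intervention assessment; Table 3)

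| Period | Intervention | Wait-list |
|---|---|---|
| Before the 5-week assessment | 1 session + 4 calls = 5 | 0 (Post-intervention assessment section) or about 1 (Participant Timeline) |
| 5-week assessment | 1 | 1 |
| Week 5 to month 6, monthly calls | 4-5 | 4-5 |
| 3- and 6-month assessments | 2 | 2 |
| Total | 12-13 | 7-9 |

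Through week 5 the count is 6 against 1-2. The whole difference arises in 5 of 26 weeks: 5/26 = 19% of follow-up. Participant Timeline does not list the 3-month visit. Without it, each total falls by one and the difference is unchanged.

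**2. Effect on an apparent rate ratio (illustration)**

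Assume an equal and constant true event rate. Let pI be the probability that an event is recorded under weekly contact and pW the probability under the sparser contact. Assume pW applies to both arms after week 5.

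- Weeks 0-5: ratio = pI / pW
- 26 weeks: ratio = (5·pI + 21·pW) / (26·pW)

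| pI, pW (assumed) | Weeks 0-5 | 26 weeks |
|---|---|---|
| 0.90, 0.80 | 0.90/0.80 = 1.13 | (4.5 + 16.8)/20.8 = 1.02 |
| 0.70, 0.40 | 0.70/0.40 = 1.75 | (3.5 + 8.4)/10.4 = 1.14 |
| 0.90, 0.50 | 0.90/0.50 = 1.80 | (4.5 + 10.5)/13.0 = 1.15 |
| 0.90, 0.30 | 0.90/0.30 = 3.00 | (4.5 + 6.3)/7.8 = 1.38 |

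The early ratio depends entirely on the assumed capture. The 26-week ratio is much closer to 1 because 21 of the 26 weeks are balanced.

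**The case against.** A reader might infer that wait-list events are picked up only through monthly calls. The documents do not support that. Phone and email are open to both arms at any time, and Table 3 marks adverse events at assessments that both arms attend.

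Nor do they state that therapists record adverse events. The adverse event item does not name the therapist calls. Capture there is an inference from the health-status content of the calls and from the during-intervention mark in Table 3. It is a reasonable inference, since the only scheduled contacts described for that phase are the therapist's, but it remains one.

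Three further points carry weight:

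- No between-arm adverse event test is named.
- With 28-35 participants per arm, chance will dominate. For an assumed 20 events per arm, treated as Poisson counts, the 95% interval for a rate ratio spans a factor of exp(1.96·√(1/20 + 1/20)) = 1.9 either way, far more than 1.14.
- The text just before the adverse event item is broken in the copy reviewed, so the absence of a scripted question can be asserted only for the text that can be read.

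These points limit the consequence but do not remove the cause. Sampling error is no reason to leave an avoidable bias in place, and rates listed as an outcome will be set side by side even without a test. Nothing readable gives the wait-list arm a matching early inquiry.

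**Conclusion.** The point holds in limited form. Before the shared 5-week assessment there are 5 scheduled staff contacts in the intervention arm against 0-1 in the wait-list arm, reporting is passive, and no equalising inquiry is described. Between-arm rates of early minor events are therefore open to ascertainment bias, most plausibly towards more events in the intervention arm.

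The size is unknown. Under the assumed capture probabilities above, the apparent ratio is about 1.1 to 3.0 in weeks 0-5. Over 26 weeks it is about 1.14 for 70% against 40% capture. These figures assume equal true rates, a constant event rate, and equal capture after week 5.

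Two stronger conclusions do not follow. The rates as a whole are not shown to be non-comparable, because the schedules match after week 5 and events needing hospitalization depend less on call frequency. Nor does contact frequency explain why this pilot could not establish relative safety; sample size would largely prevent that even with perfect ascertainment. This is an inexpensive improvement worth making, and it does not affect the primary analyses.

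**What to change.** In the adverse event item under Secondary outcomes:

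1. Add one short fixed question set (for example falls, injuries, symptomatic hypoglycemia, emergency visits and hospital stays). The research assistant asks it in both arms at the contacts they share: the 5-week assessment, the monthly calls, and the 3- and 6-month assessments.
2. Use a common recall window running from the previous shared contact.
3. Apply it to all adverse events, not only those judged study-related. Relatedness to the intervention hardly applies to the wait-list arm before month 6.
4. Record the route by which each event was first reported.
5. Base the main between-arm rate of minor events on answers at the shared contacts. Count serious events from any route in both arms, so that someone who phones in a serious event and then drops out is not lost. Also report rates with all routes included.

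Reconcile Participant Timeline with the Post-intervention assessment section on when the wait-list monthly calls start. State also whether the 3-month assessment takes place, since Participant Timeline omits it.

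The cost is a few protocol lines and one short form at contacts already scheduled, with no extra staff or visits. Minor events known only from therapist calls leave the main comparison, but they are still listed and acted on. Some bias may remain, because a participant who has already discussed an event with the therapist may recall it better at week 5.

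### Serious and minor grades are given only to adverse events judged study-related, by an undefined judgment, so the graded rates are not comparable between arms

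*Combined protocol and SAP*

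**What the plan says.** The adverse event item under Secondary outcomes (Measures) collects events without restriction by cause or arm: "Participants can report an AE event by phone or email or at the monthly follow-up phone calls", and "The AEs will be tracked electronically in a participant management system". Grading is narrower. "Study-related AEs will be classified as serious if they require hospitalization or result in significant disability", and then "All other study-related AEs will be classified as minor, resulting in minimal or no disability and not requiring hospitalization". An event judged unrelated has no category. The item does not say who decides relatedness, by what criteria, or whether that person knows the arm.

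Table 3 lists adverse events among the secondary outcomes and schedules them at post-intervention, during the intervention, and at 3 and 6 months, without separating the arms.

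On exposure, Participant Timeline says: "The wait-list control group will receive monthly phone calls to discuss about their health status but not PA-related issues". The section on the wait-list control group adds: "This group will participate in all outcome assessments as the intervention group at baseline, post-intervention, and 3-months and final assessments". After the 5-week assessment, "a RA will contact all participants monthly until the 6-month final assessment to discuss changes in medications and health status". Before that, in the intervention arm only, "the same OT will make weekly phone calls to the participants for 4 weeks", and those calls also cover health status.

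The Statistical Analysis section contains no adverse event analysis. Its secondary analyses name functional status, biomarkers and quality of life.

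**The concern.** Relatedness is a judgment made after randomization, and the treatment received can influence it. The intervention encourages people to move more in daily life; one worked example in the protocol has a participant climbing stairs while waiting at a clinic. A fall on the stairs can readily be linked to the study in that arm. In the control arm the same fall has no activity advice behind it. If only events that pass this filter are graded, the graded counts mix what happened with how it was attributed.

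The error can run either way. Background events may be credited to the intervention and create an apparent excess. Or intervention-arm falls may be put down to age or co-morbidity and hide a real one.

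The protocol itself notes that more intense activity may raise injury risk. It also describes falls, co-morbidity and mobility limitation as common in older people with diabetes. Attributing single events is hard in such a group, and the randomized control arm is the natural way to separate background from effect. The pilot is also meant to prepare a larger trial, for which usable safety rates would be a natural product.

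**Working it through.** The documents give no adverse event rate, safety sample size or power, so there is no stated figure to reproduce. The check compares the rules and then illustrates their effect on assumed rates.

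**Rules side by side**

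1. Collection: all adverse events, both arms.
2. Grading: study-related events only.
3. Exposure: both arms have the assessments; only one has the activity counseling.
4. Analysis: no adverse event comparison, graded or ungraded.

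Steps 2 and 3 together make the probability of being graded depend on arm. Step 4 means that no other planned summary corrects this.

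**Inputs**

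- From the documents: N = 70 and 28–35 per group. With equal arms, 70 / 2 = 35. Also 28 / 35 = 0.80, which fits the stated range if 20% loss is assumed; no dropout rate is given.
- Assumed: background event risk b of 10–30%, the same in both arms. Probability that a background event is called study-related: 30–50% in the intervention arm (a_I) and 0–5% in the control arm (a_C).

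**No true excess**

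Expected graded count = n × b × a; expected count of all events = n × b.

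- Intervention, n = 35: from 35 × 0.10 × 0.30 = 1.05 to 35 × 0.30 × 0.50 = 5.25.
- Control, n = 35: from 0 to 35 × 0.30 × 0.05 = 0.525.
- All events, n = 35: 3.5 against 3.5 at 10%, 7.0 against 7.0 at 20%, 10.5 against 10.5 at 30%.
- At n = 28, the graded counts are 28 × 0.10 × 0.30 = 0.84 to 28 × 0.30 × 0.50 = 4.2, against 0 to 28 × 0.30 × 0.05 = 0.42.

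The apparent excess comes entirely from a_I exceeding a_C. With equal attribution the expected graded counts would be equal.

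**Real excess hidden**

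Take n = 35, a control risk of 20% and an intervention risk of 30%. All events: 35 × 0.30 = 10.5 against 35 × 0.20 = 7.0, a difference of 3.5. If only 5% of events in either arm were called study-related, graded counts would be 10.5 × 0.05 = 0.525 against 7.0 × 0.05 = 0.35, a difference of 0.175.

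**Serious events**

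On an assumed 6-month hospitalization risk of 5–15%, the expected total is 70 × 0.05 = 3.5 to 70 × 0.15 = 10.5. Half of these, 1.75 to 5.25, would be in controls. Whether each is graded serious turns on the relatedness judgment.

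**What complete grading could show**

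Power of a two-sided Fisher test at an assumed 0.05 level, with all events counted and 28–35 per arm:

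| Excess | Control risks assumed | Power |
|---|---|---|
| 10 points | 10%, 20% | 8–13% |
| 20 points | 10%, 20%, 30% | 24–46% |

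**The case against.** The strongest reply is that the plan loses no data. Events are tracked in both arms, both arms get monthly health-status calls, and Table 3 has no relatedness filter. An all-event comparison by arm could be made, and hospitalizations could be graded later if the records hold enough detail. This stands. A reader might infer that a true excess cannot be told from background anywhere in the trial; the documents do not support that. The problem is confined to the graded rates.

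A reader might also infer that control events would almost never be graded. That is not established. Controls do the same walk tests, blood sampling and home monitoring, so some of their events could be study-related. Nor do the documents say that relatedness is judged by staff who know the arm; they leave it unspecified.

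The assumed rates are also open to challenge. Eligibility excludes recent hospitalization, medical instability, recent bed rest, recent heart attack and recent joint replacement, which may favor the lower end of the hospitalization range.

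Finally, no between-arm comparison of graded rates is planned, and at 28–35 per arm any safety comparison has low power. Both points are right. They limit what the pilot can conclude. They do not make the graded rates, the only ones the plan defines by seriousness, interpretable by arm.

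**Conclusion.** The point holds in a limited form. Serious and minor grades depend on a relatedness judgment with no stated assessor, criteria or blinding, in a design where only one arm has an activity intervention to blame. The graded rates are therefore not comparable between arms, and the direction of the error cannot be predicted.

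Its size is unknown because the documents give no event rate. The illustration of about 1.1 to 5.3 graded events against 0 to 0.5, with no true difference and 35 per arm, rests wholly on the assumed risks and attribution probabilities. The efficacy aims are unaffected. Even with the change, the safety comparison would be descriptive. This is a cheap improvement, not a flaw that undermines the trial.

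**What to change.** In the adverse event item under Secondary outcomes:

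- Remove the study-related condition from both grading sentences, so that every tracked event in either arm is graded whatever its cause.
- Record relatedness as a separate field. State who judges it and by what criteria, and keep that person blind to arm where existing staff make this feasible.

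In the Statistical Analysis section, add a table of all adverse events and serious adverse events by randomized arm, with confidence intervals, labeled descriptive. Give the study-related subset in a second table.

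In the report, note that the four extra weekly calls in the intervention arm make early ascertainment unequal; grading all events does not remove this.

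The cost is two edited sentences, one field in the existing tracking system and the added tables. The downside is somewhat more events to grade and a serious-event count that looks higher. No treatment or clinical rule changes.
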